Maurer et al. (2014) [Germany]. The purpose of this retrospective study was to investigate the diagnostic efficacy of Ga PSMA-HBED-CC -PET imaging when compared against radical prostatectomy, templated lymph node dissection, and conventional imaging (CT, MRI). The primary inclusion criterion was intermediate-to-high risk prostate cancer scheduled to undergo radical prostatectomy. The only exclusion criterion was presence, or history, of a secondary malignancy. A total of 130 patients were reviewed. A contrast enhanced diagnostic CT was performed at the same imaging session as the PET scan. A double-trained board certified radiologist-nuclear medicine physician blinded to post-operative histopathological results analyzed all the imaging data sets (Ga PSMA-PET/CT and PET/MR). Conventional imaging was read prior to the Ga PSMA-PET data. Results yielded a patient-based ROC AUC of 0.835 (95% CI 0.763 – 0.908) for Ga PSMA-PET and an AUC of 0.691 (95% CI 0.592-0.789) for conventional imaging. For Ga PSMA-PET patient-based sensitivity was 65.9 %, specificity was 98.9%, and overall accuracy of 88.5%. In contrast, conventional imaging had a patient-based sensitivity of 43.9%, specificity of 85.4%, and an overall accuracy of 72.3%. On a template-based analysis driven by lymph node dissection, the Ga PSMA-PET sensitivity was calculated as 78.2%, specificity as 99.1%, and accuracy as 95.7%. Conventional imaging resulted in a sensitivity of 29.1%, specificity of 97.2%, and accuracy of 86.1%.

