Van Leeuwen et al. (2014) [Australia]. The purpose of this prospective trial was to assess accuracy of Ga PSMA-HBED-CC -PET/CT for lymph node staging in intermediate- and high-risk prostate cancer. Criteria for selection included planned radical prostatectomy, treatment naïve, negative bone scan, no concurrent (or history of) a secondary malignancy, and at >5% risk of metastatic lymph nodes. Patients with suspected extra-nodal disease on prior contrast-enhanced CT were excluded. Ga PSMA-HBED-CC PET/CT was performed <4 weeks before the radical prostatectomy and lymph node dissection. A total of 30 men were enrolled and evaluated. A non-contrast enhanced CT was performed at the same imaging session of the Ga PSMA-HBED-CC -PET. Images were analyzed by two nuclear medicine physicians; it is not stated if the physicians were blinded to the pathologic results or if the scan interpretations were completed prior to surgery. Results yielded a patient-based specificity of 95%, sensitivity of 64%, positive predictive value of 88%, and negative predictive value of 82%. Lymph node analysis yielded specificity of 100%, sensitivity of 58%, PPV of 94% and NPV of 98%. The mean size of true-positive metastatic lymph nodes was 4.7 mm ( $\pm$  1.4mm) and false-negative size was 2.7mm ( $\pm$  1.3mm).

Eiber et al. (2015) [Germany]. The purpose of this retrospective study was to investigate the detection rate of Ga PSMA-HBED-CC PET/CT in men with

biochemical recurrence (PSA  $\geq$  0.2 ng/mL). Only men who had undergone a radical prostatectomy, had not received chemotherapy, and had a diagnostic CT done with the PSMA imaging study were included. Men undergoing antiandrogen therapy (n=70) were included. A total of 248 subjects were included in the analysis. The active comparator was the diagnostic CT done simultaneously with the PET imaging. Scans were interpreted by a board certified radiologist and a board certified nuclear medicine physician. The reviewers were not blinded. No significant detection effect was observed with antiandrogen use ( $p=0.0783$ ). PSMA was able to identify additional areas of disease involvement in 61 subjects (24.6%) whereas CT showed additional regions in 17 subjects (6.9%). A significant limitation of the study was a lack of histopathology for outcome comparisons. Sensitivity, specificity, positive and negative predictive values are not provided.

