## 13. STATISTICAL CONSIDERATIONS

### 13.1. Statistical Justification

This study is a pilot study to determine target sensitivity for Ga PSMA-HBED-CC for the detection of prostate cancer in the pre-prostatectomy population. Based upon literature, we anticipate sensitivities of > 80% in this patient population, but there are uncertainties, particularly related to the proposed reference standard. We plan to use the results of this pilot study, potentially combined with reported results from other sites across the US performing similar studies (same patient population, same methods, same reference standard definitions...) to determine most-appropriate primary endpoint sensitivities for a larger University of Iowa study to follow this one, so as to appropriately statistically power the larger study.

The primary objective of this pilot study is to obtain preliminary information on the sensitivity of physician reads for Ga-68 PSMA pre-prostatectomy; physicians' ability to correctly identify prostate cancer and metastases via Ga-68 PSMA relative to our pathology/conventional imaging reference standard. Due to the lack of clinical experience with this radiopharmaceutical, this pilot study is meant to gain meaningful information of the sensitivity of this agent in this patient population to generate hypotheses for further trials.

To evaluate sensitivity, patients must undergo both Ga-68 PSMA imaging and evaluation for prostate cancer by pathology, follow-up conventional imaging, or both. Sensitivity is defined as:

$$Sensitivity = \frac{\text{number of true positives (TP)}}{\text{number of true positives (TP)} + \text{number of false positives (FP)}}$$

The table below provides 95% confidence interval half-widths for a range of sensitivity values based on a planned sample size of 30 patients using a normal approximation.

Sensitivity	Half-Width
70%	16.4%
75%	15.5%
80%	14.3%
85%	12.8%
90%	10.7%

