### 13.2. Primary Endpoint:

The sensitivity, specificity, positive and negative predictive values of Ga PSMA-HBED-CC PET/CT for the detection of disease on a per patient basis will be summarized by descriptive statistics.

No statistical significance will be generated due to the pilot nature of the project.

The below criteria will be used for evaluation of a per patient basis with nodal regional correlation (Primary endpoint 1):

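### The Wald half-widths in 13.1 break down in the 90% row (upper limit 100.7%, coverage about 81%), and 13.2 names no interval method for the final estimates

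*Combined protocol and SAP*

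**What the plan says.** Section 13.1 justifies the sample size by precision. It tabulates "95% confidence interval half-widths for a range of sensitivity values based on a planned sample size of 30 patients using a normal approximation": 16.4, 15.5, 14.3, 12.8 and 10.7 points for sensitivities of 70, 75, 80, 85 and 90%. The same section states "we anticipate sensitivities of > 80% in this patient population", so the upper rows are the ones the plan expects to matter. It adds that the results, possibly pooled with those of other sites, will help set the target sensitivity for a larger study.

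Section 13.2 says that per-patient sensitivity, specificity, PPV and NPV "will be summarized by descriptive statistics", without significance testing. It names no interval method. The plan states no expected specificity. Section 2.3 reports per-patient specificities of 98.9% (retrospective study, 130 patients) and 95% (prospective study, 30 men) as background.

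**The concern.** The Wald interval is symmetric about the estimate and takes its standard error from the estimate itself. Near 100% the standard error is too small and the upper limit can pass 100%. At exactly 100% the interval has no width. The plan expects sensitivity above 80%, and the cited specificities are close to 100%.

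A pilot justified by precision has the interval as its main statement of what was learned. If the lower limit is too high, the pilot appears to rule out sensitivities that it has not ruled out, and the planners of the larger study may take an optimistic target from it. Because 13.2 names no method, the analyst may give no interval or fall back on the one in 13.1.

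**Working it through.** **Inputs.** n = 30, 95%, normal approximation and the five sensitivities are from 13.1. The level is taken as two-sided, z = 1.96. The background specificities are from 2.3.

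**1. The plan's figures.** Half-width = 1.96 × √(p(1−p)/30). At p = 0.90: 1.96 × √(0.09/30) = 1.96 × 0.05477 = 10.7 points. All five rows reproduce.

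**2. Implied limits and exact coverage at n = 30.** Coverage is the sum of Binomial(30, p) probabilities over every count x whose Wald interval contains p.

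| True p | Half-width | Wald limits | Exact coverage |
|---|---|---|---|
| 70% | 16.4 | 53.6 to 86.4% | 95.3% |
| 75% | 15.5 | 59.5 to 90.5% | 94.1% |
| 80% | 14.3 | 65.7 to 94.3% | 94.6% |
| 85% | 12.8 | 72.2 to 97.8% | 94.2% |
| 90% | 10.7 | 79.3 to 100.7% | 80.9% |

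**3. Where the 90% row misses.** At 29/30 the Wald lower limit is 90.2%, and at 30/30 the interval is 100% to 100%. Both exclude a true 90% from above: 14.1% + 4.2% = 18.4% after rounding. At 22/30 or fewer the upper limit is below 90%, with probability 0.8%. Total non-coverage is 19.1%, almost all of it over-optimistic.

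**4. Is 80.9% representative?** Only partly. Because 29/30 has a lower limit of 90.2%, coverage is 80.0% at p = 0.902 and 94.7% at p = 0.903. Averaged over true values of 80% to 95%, coverage is about 89%, with a minimum of 78%. Over 70% to 85% it averages about 92%.

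**5. Better limits at n = 30.** Wilson: [p̂ + z²/2n ± z√(p̂(1−p̂)/n + z²/4n²)] / (1 + z²/n). For 27/30: (0.9640 ± 0.1250)/1.1280 = 74.4% to 96.5%. Clopper-Pearson gives 73.5% to 97.9%. Exact coverage at a true 90% is 97.4% for Wilson and 99.2% for Clopper-Pearson.

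**6. If Wald were carried to 13.2.** Each measure has its own, smaller denominator, which the plan does not give. The prospective study's percentages fit 11 node-positive and 19 node-negative men (7/11 = 64%, 18/19 = 95%). The retrospective study's accuracy implies a node-positive share of (98.9 − 88.5)/(98.9 − 65.9) = 31.5%, or about 9.5 of 30. I therefore assume 10 positive and 20 negative.

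- Sensitivity, 10 positive: Wald coverage is 88.8% at a true 65%, 88.6% at 80% and 65.0% at 90%. At 90% most of the loss is the 0.90¹⁰ = 34.9% chance of 10/10, where the width is zero.
- Specificity, 20 negative: the chance of no false positive is 0.95²⁰ = 36% at a true 95% and 0.989²⁰ = 80% at 98.9%. Wald then gives 100% to 100%. Clopper-Pearson gives a lower limit of 0.025^(1/20) = 83%. Overall Wald coverage is 64% and 20%.
- Range: with 19 negative the zero-width chances are 38% and 81%; with all 30 negative they are 21% and 72%.

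**The case against.** The table is arithmetically correct and says openly that it is an approximation. Four rows of five have essentially nominal coverage at their tabulated values, and the fifth passes 100% by 0.7 point. As a planning answer the half-widths hardly move: Wilson gives 15.6, 13.9 and 11.1 points at 70, 80 and 90%, against 16.4, 14.3 and 10.7. The point estimate is the same under any method, there is no test or decision rule, and 13.1 does not say that a lower limit will set the later target. All of this stands, and it limits the severity.

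It does not remove the point. What changes is the position of the interval rather than its width: the lower limit for 27/30 falls from 79.3% to 74.4% or 73.5%. Ruling out significance tests does not rule out intervals.

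A reader might infer more than the documents support:

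- That the approximation fails across the table. At the tabulated values it fails only in the 90% row.
- That 81% is typical coverage. It lies near a trough caused by discreteness.
- That the interval collapses at the expected specificity. The plan states no expected specificity and does not say Wald will be used for it. At 95% and 98.9% the Wald half-widths at n = 30 are positive, 7.8 and 3.7 points. Zero width needs an observed 100%, which is likely at a true 98.9% but not at 95%.

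**Conclusion.** The point holds in limited form. The 90% row of 13.1 states a 95% interval that includes impossible values and covers 80.9% of the time, with errors almost entirely on the optimistic side; over true values of 80% to 95%, coverage averages about 89%. These results need only the plan's own n = 30.

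The worse behaviour on smaller groups is conditional. It assumes that Wald is carried into 13.2, which the plan does not say, and it uses assumed denominators of 10 and 20 and background specificities. It shows why a method should be named. It does not show that the planned analysis is wrong.

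In a descriptive pilot this is a should-fix. It is separate from the question of whether 30 is the right denominator for sensitivity; naming a better interval does not settle that.

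**What to change.** **Section 13.1.** Replace the half-width column with lower and upper limits from one named method. Since 75% and 85% of 30 are not whole patients, rows at attainable counts are cleaner:

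| Observed | Wald | Wilson | Clopper-Pearson |
|---|---|---|---|
| 21/30 (70.0%) | 53.6 to 86.4% | 52.1 to 83.3% | 50.6 to 85.3% |
| 23/30 (76.7%) | 61.5 to 91.8% | 59.1 to 88.2% | 57.7 to 90.1% |
| 24/30 (80.0%) | 65.7 to 94.3% | 62.7 to 90.5% | 61.4 to 92.3% |
| 26/30 (86.7%) | 74.5 to 98.8% | 70.3 to 94.7% | 69.3 to 96.2% |
| 27/30 (90.0%) | 79.3 to 100.7% | 74.4 to 96.5% | 73.5 to 97.9% |

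**Section 13.2.** Add one sentence: sensitivity, specificity, PPV and NPV are each reported with a two-sided 95% interval by that method, on their own denominators, with numerator and denominator shown.

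Either method serves. Clopper-Pearson never covers below 95% but is wider. Wilson is narrower and can dip slightly below (93.0% at a true 70% with n = 30, and at a true 90% with n = 10).

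**Cost.** A restated table and one sentence, with no extra patients or procedures. Lower limits at n = 30 look about 1 to 6 points less favourable (70%: 53.6 − 52.1 = 1.5 points with Wilson; 90%: 79.3 − 73.5 = 5.8 points with Clopper-Pearson).

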### 13.2. Primary Endpoint:

The sensitivity, specificity, positive and negative predictive values of Ga PSMA-HBED-CC PET/CT for the detection of disease on a per patient basis will be summarized by descriptive statistics.

No statistical significance will be generated due to the pilot nature of the project.

The below criteria will be used for evaluation of a per patient basis with nodal regional correlation (Primary endpoint 1):

#### 13.2.1. True positive patient:

13.2.1.1. **Ga PSMA-HBED-CC PET/CT positive for a regional node by internal blind reader:** pathology at prostatectomy is positive for a regional node that correlates in location to the PET images (location on pathology is determined by the urologist at the time of the surgery). Only one node needs to correspond between imaging and pathology for a patient to be considered a true positive.

13.2.1.2. **Ga PSMA-HBED-CC PET/CT positive for regional nodes by internal blind reader,** pathology negative for regional nodes, imaging after prostatectomy demonstrates the same node was not removed at surgery, and follow-up biopsy or imaging demonstrates presence of nodal disease as defined in Section 12.2.1.2 .

13.2.1.3. **Conventional imaging criteria for positive node on follow-up imaging:** imaging within 3-12 months, the node decreases by more than 30% (for patients undergoing systemic treatment or focal therapy at this site) or increase by more than 20% in short axis diameter in the absence of treatment (with a minimum of 3 mm in change in size) as defined in Section 12.2.2.1 .

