#### 5.1. Imaging preparation

- 5.1.1. **Oral hydration.** Participants will be encouraged to maximize hydration the day before and day of  $^{68}\text{Ga}$  PSMA-HBED-CC imaging.
- 5.1.2. **Furosemide.** 20 mg furosemide (IV push) will be administered concurrently or immediately after radiotracer administration to minimize PET scatter artifacts from excreted radiotracer accumulation in the kidney and urinary

bladder.

- 5.1.3. **Contrast.** Imaging contrast will not be ordered as part of this study.
- 5.1.4. **Voiding.** Participants will be asked to void their bladder immediately prior to radiotracer injection and before imaging.

5.2. **Ga PSMA-HBED-CC administration**

- 5.2.1. **Dose.** 3-7 mCi (111 – 259 MBq). Target 5 mCi.
- 5.2.2. **Route of administration.** Intravenous.
- 5.2.3. **Frequency.** Once per PET scan.
- 5.2.4. **Uptake time.** 75 minutes ± 25 minutes. Target 75 minutes

5.3. **Prohibited Medications**

None.

5.4. **PET/CT Imaging Procedures**

- 5.4.1. **Scan coverage.** Scan coverage will extend from mid-thigh to the base of the skull, starting from the mid-thighs to prevent urinary bladder radiotracer accumulation at the start of PET imaging. Subject to void immediately prior to imaging.
- 5.4.2. **Bed position.** Scan time will be dependent on scanner capabilities. At a minimum, 3 minutes per bed position will be used.
- 5.4.3. **Discharge.** Subject must be monitored for adverse events for a minimum of 2 hours post-injection.
- 5.4.4. **Local Analysis.** A board-certified nuclear medicine physician on-site will interpret the images within 3 business days of the imaging study. These interpretations will not be used for final evaluation, however regional positivity results will be collected as study data.
- 5.4.5. **Internal Blinded Reads.** Imaging data will be interpreted by two different readers in a random order at separate reading sessions. Cross sectional imaging from the PET will be available for anatomic correlation. Final reads for each subject will be interpreted as positive or negative for the presence of pelvic nodal disease, and positive or negative for the presence of osseous metastatic disease and soft tissue metastases outside of the pelvis. All readers will have undergone Ga PSMA PET training.
- 5.4.6. **Results dissemination.** Results will be shared with the subject's urologist and will be included in the subject's medical record.

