## 5.6. **Post-Imaging Prostatectomy**

Prostatectomy and pelvic nodal dissection will be performed at the discretion of referring physician after reviewing imaging results. Nodal dissection should follow standard of care.

- 5.6.1. **Negative imaging.** Subjects without evidence of positive nodal or metastatic disease on  $^{68}\text{Ga}$  PSMA-HBED-CC PET imaging will undergo radical prostatectomy and pelvic nodal dissection. The pelvic nodal dissection will be performed regardless of imaging results.
- 5.6.2. **Positive imaging.** The urologist will be informed of the location of any  $^{68}\text{Ga}$  PSMA-HBED-CC PET positive (or suspicious) regional pelvic nodes prior to surgery. The surgeon should attempt to capture the suspicious node during the nodal dissection.
- 5.6.3. **Nodal dissection.** Nodes will be marked by location using the standard procedures. For example, if the urologist removed left and right nodal regions separately, the subject will have two nodal regions (left/right). If the nodes are removed in six groups (bilateral internal/external/obturator nodes), the subject will have six nodal regions analyzed.
- 5.6.4. **Pathology:** Specimens from prostatectomy will be evaluated for the presence of nodal metastasis. This will be reported on a per patient basis, and by region as positive or negative. The pathology report should list the number of nodes counted during the exam.
- 5.6.5. **Immunohistochemical staining (IHC) (optional).** Although not routinely performed during standard practice, IHC staining for PSMA of tumor specimens (primary and lymph node metastases) is preferred.

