## 6.4. **Follow-up**

6.4.1. **Pathology.** Results from pathology ordered per standard of care up to 12 months post Ga PSMA-HBED-CC PET/CT, will be obtained for study analysis.

6.4.2. **Follow-up imaging.** Conventional imaging ordered per standard of care up to 12 months post Ga PSMA-HBED-CC PET/CT, will be obtained for study analysis. If the 1st Ga-68 PSMA-HBED-CC PET/CT scan shows lesions outside the pelvic region AND if imaging is NOT obtained per standard of care the research study will obtain a CT (abdomen and pelvis w/ contrast if contrast not contraindicated). Readers will be unblinded to all results and will be specifically informed of the location of the Ga PSMA-HBED-CC PET positive lesions so follow-up measurements may be performed on the same lesions.

6.4.3. **Laboratory.** Results from laboratory reports related to prostate cancer monitoring (e.g. PSA levels) ordered per standard of care up to 12 months post Ga PSMA-HBED-CC PET/CT, will be obtained for study analysis.

6.4.4. **Second Ga PSMA-HBED-CC PET/CT (if medically indicated).** If the 1st Ga PSMA-HBED-CC PET/CT scan shows lymph nodes or visceral (soft tissue) lesions positive for prostate cancer disease, but surgery or biopsy results in negative pathology; the subject may be asked to return to complete a 2nd Ga-68 PSMA-HBED-CC PET/CT imaging visit.

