## 12.2. Reference standard definition:

12.2.1. Histopathology/Biopsy will be the primary determinate of tissue positivity and negativity for prostate cancer disease. Pathology date, organ, and location as well as any notes related to the pathology will be obtained from the subject chart. The anatomical region/sub-region the pathology occurred in will be assigned by the investigator team:

Ga-PSMA-HBED-CC positive findings are aimed to be confirmed by histopathology/biopsy if clinically feasible. Pathology performed 60 days before or after the Ga-PSMA-HBED-CC PET will be available for correlation.

Histopathological procedures and biopsies will be performed as clinically indicated and as per institutional protocol.

12.2.1.1. Lymph Nodes, Visceral Lesions, and Bone Lesions positive for disease by pathology.

- Lesions with positive pathologic confirmation will be regarded as positive for disease. The regionality of the resected tissue will be assigned into respective regions and sub-regions as described above in Table 12.2.

12.2.1.2. Lymph Nodes and Visceral Lesions negative for disease by pathology.

- Tissue removed and negative for pathology are considered negative for prostate cancer disease, unless subsequent conventional imaging or Ga-PSMA-HBED-CC PET imaging demonstrates that targeted tissue were not resected. In this case:

- i. Subjects can be rescanned with dedicated CT, MRI, or Ga-PSMA-HBED-CC PET/CT to determine if the suspicious Ga-PSMA-HBED-CC tissue was removed. If the tissue is confirmed as removed, this is considered negative for disease.

ii. If  $^{68}\text{Ga}$ -PSMA-HBED-CC PET/CT positive tissue is still present, a needle biopsy can be pursued at the discretion of the treating physician. Images of the procedure will be reviewed to determine if the correct tissue was biopsied.

- If the  $^{68}\text{Ga}$ -PSMA-HBED-CC PET/CT positive tissue was biopsied, a negative pathologic finding of the biopsied tissue is considered negative for disease.
- If the  $^{68}\text{Ga}$ -PSMA-HBED-CC PET/CT positive tissue was biopsied, a positive pathologic finding of the biopsied tissue is considered positive for disease.
- If biopsy or re-biopsy is not performed, or the wrong tissue was biopsied, change in node size as measured by conventional imaging and as defined below will be the criteria by which disease status will be defined.

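### The step that matches node location on pathology to the PET is not masked to the PET result, so the true-positive versus false-positive call can lean toward the scan

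*Combined protocol and SAP*

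**What the plan says.** **Who is masked.** Section 12.1 withholds all other imaging and clinical data from the two blinded PET readers. It is the only masking rule in the protocol. The local read is kept out of the final evaluation (5.4.4), but it goes to the clinic: "Results will be shared with the subject's urologist and will be included in the subject's medical record" (5.4.6).

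**Who sets location.** Under 5.6.2, "The urologist will be informed of the location of any" "PET positive (or suspicious) regional pelvic nodes prior to surgery", and "The surgeon should attempt to capture the suspicious node during the nodal dissection". Section 13.2.1.1 then says of the pathology side of the match that "location on pathology is determined by the urologist at the time of the surgery". Section 12.2.1 takes pathology details from the subject's chart and adds: "The anatomical region/sub-region the pathology occurred in will be assigned by the investigator team". It does not say whether that team has seen the PET.

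**What location decides.** Under 13.2.1.1 a PET-positive man with a positive node in a corresponding location is a true positive, and one corresponding node is enough. Under 13.2.3.2 a PET-positive man whose positive node lies in a different nodal region is a false positive.

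**Follow-up imaging.** Section 12.2.2 assigns this to a local read. Section 6.4.2 says "Readers will be unblinded to all results and will be specifically informed of the location" of the PET-positive lesions, and gives as the reason that the same lesions can then be measured.

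**The concern.** Masking the index test protects the PET reads from the reference standard. It does nothing in the other direction. Here the location half of the reference standard is set by people who know, or are free to know, where the scan was positive.

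That matters because the match is a judgement in some patients. A packet labelled only left or right has to be set against seven PET subgroups, and the subgroup for other pelvic nodes has no counterpart in either dissection example in 5.6.3. The level of matching is also not settled. Section 12.1.1.1 says pelvic sub-region data will not be used directly for the primary endpoint, yet 1.1.1 asks for nodal regional correlation and 13.2.3.2 needs a different nodal region to exist. The looser the rule, the more room an unmasked assigner has.

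The expected direction is upward. Doubtful cases would tend to be resolved toward the PET site, which turns false positives into true positives. The estimate is the product of this pilot: 13.1 says it will help choose the target sensitivity for a larger study, and 2.4 says the data are meant to support further approvals.

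**Working it through.** **The plan's own figure.** The documents give no rate of location misjudgement, so there is nothing to reproduce on this exact point. The only precision figures are the 95% half-widths in 13.1. They reproduce: for a sensitivity of 80%, 1.96 × √(0.80 × 0.20 / 30) = 14.3%. They describe sampling error only and say nothing about bias in the reference standard.

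**Where the two facts meet.**
1. The surgeon labels packets at operation knowing the PET site (5.6.2) but before nodal histology is reported.
2. The investigator team takes pathology location from the chart (12.2.1), and the PET result is in the same record (5.4.6).
3. So at the mapping step both the PET site and the positive packet can be in view, and no passage prevents it.

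**Illustrative table.** Section 2.3 reports a 30-man prospective study with per-patient sensitivity 64%, specificity 95%, PPV 88% and NPV 82%. The whole-number table that fits is TP 7, FP 1, TN 18, FN 4:
- sensitivity 7/11 = 63.6%
- specificity 18/19 = 94.7%
- PPV 7/8 = 87.5%
- NPV 18/22 = 81.8%

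**Reclassification.** Suppose k of the 7 matches were really mismatches. Under 13.2.3.2 each moves from TP to FP:
- PPV = (7 − k)/8
- sensitivity = (7 − k)/(11 − k)
- specificity = 18/(19 + k)

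| k | PPV | Sensitivity | Specificity |
|---|---|---|---|
| 0 | 87.5% | 63.6% | 94.7% |
| 1 | 6/8 = 75.0% | 6/10 = 60.0% | 18/20 = 90.0% |
| 2 | 5/8 = 62.5% | 5/9 = 55.6% | 18/21 = 85.7% |
| 3 | 4/8 = 50.0% | 4/8 = 50.0% | 18/22 = 81.8% |

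Sensitivity here is TP/(TP + FN). Section 13.1 prints a different denominator, which is a separate matter. The range k = 0 to 3 is an assumption, and the documents do not say which value is likely. Each judgement moves PPV by 12.5 points, and the first moves sensitivity by 3.6.

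**Size change, primary endpoint.** Reaching the size criterion can make a man a true positive (13.2.1.2, 13.2.1.3). Missing it leaves the region indeterminate (12.2.2.1) and the man non-evaluable (13.2.5.1). A false positive under 13.2.3.1 instead needs negative pathology and a node that is gone. One extra TP by size gives PPV 8/9 = 88.9% and sensitivity 8/12 = 66.7%, rises of 1.4 and 3.0 points.

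**Size change, secondary endpoints.** Here size can separate true from false positive: 13.3.1 counts a region positive by the 12.2.2 rules, and 13.3.3 counts a PET-positive region as false when imaging is not positive.

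**The case against.** The strongest defence is that discretion is limited. Location is recorded at surgery by standard procedures, before histology is known. Where packets are only left or right, a wrong match needs a wrong side. The surgeon knows the local read, not the blinded reads that are scored. Directing the surgeon to the suspicious node also improves verification legitimately. And this is a 30-patient descriptive pilot whose section 13.1 already admits uncertainty about the reference standard. All of that stands as a limit on size. It does not remove the defect: the local and blinded reads come from the same scan, the mapping step has no mask, and a caveat in 13.1 does not correct the estimate.

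Four stronger readings are tempting, and the documents do not support them.
- **That agreement is inflated.** A reader might infer this as fact. The documents give no misjudgement rate, so only possible upward bias is supported.
- **That 12.2.1 and 13.2.1.1 contradict each other on who assigns location.** They read naturally as two steps: the surgeon records and the team maps. The gap is that neither step is masked.
- **That size change decides true versus false positive in the primary endpoint.** It separates true positive from non-evaluable.
- **That a difference of about 1 mm can flip a patient.** At the 4.7 mm mean size of true-positive nodes in the 30-man study, 30% is 1.4 mm and 20% is 0.9 mm, and the systemic-treatment rule in 12.2.2.1 has no 3 mm minimum. But that rule also needs PSA to fall by more than 50% or rise by more than 25%, which a reader cannot shade. Section 13.2.1.3 also states a 3 mm minimum, and 2.3 does not say that 4.7 mm is a CT or MRI short axis.

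**Conclusion.** The point holds for location. The PET readers are masked, but neither the PET-informed urologist who records node location nor the team that assigns the analysis region is masked, and that location decides true versus false positive. Sensitivity and PPV can be biased upward by an unknown amount. In a table of the size this trial can expect, one patient is worth 12.5 points of PPV and about 4 points of sensitivity. This rests on two assumptions: that the trial's table resembles the one implied by the 30-man study, and that at least one match turns on judgement.

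For size measurement the point is secondary and bears mainly on the region endpoints in 13.3. Readers need the lesion location to measure the same lesion. They do not need PSA or pathology for that, yet 6.4.2 gives them everything.

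**What to change.** **Main change, in 12.2.1 and 13.2.1.1.** State three things:
1. The source of location is the specimen label recorded at surgery and in the pathology report.
2. A study team member who has not seen any PET result maps that label to the analysis region. Since the PET result is in the chart, give this person the label and pathology report as an extract.
3. The mapping is locked before the blinded reads are merged.

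The urologist may still be told the PET result, and 5.6.2 is untouched.

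**Secondary change, in 6.4.2, mainly for 13.3.** Where existing staff allow, give those making the study size measurements the lesion location only. Record millimetres, and have study staff apply the PSA and size thresholds of 12.2.2 afterwards.

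**Cost.** The main change is wording plus an order-of-operations step for existing staff, with no added scan and no change in care. The secondary change may need a separate reader, because follow-up imaging is read locally and the clinical reader may also be the measurer. That is why it is worded as conditional. Some PET knowledge will remain in the surgeon's labelling and in the local clinical read of follow-up imaging, and the report should say so.
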